6.2.2 AVOIDANCE OF ADDITIONAL ANTIPLATELET MEDICATIONS

Investigators should not prescribe or administer additional antiplatelet medications to subjects, except in the instance in which the subject has met the primary study endpoints.

6.3 SCREENING AND ENROLLMENT

All patients who are screened for eligibility will be documented in the PREVENT II Screening Log and assigned a Screening ID number. To protect patient privacy, no identifying information will be recorded.

The Sponsor may request copies of the Screening Log throughout the study, but the ongoing log will be maintained on site.

Patients who qualify to participate in the study will be approached to discuss the study, consider voluntary participation, and, if applicable, provide informed consent. For patients who do not qualify to participate in this study, the reason for ineligibility will be entered in the screening log. For enrolled subjects, the assigned Subject ID number will be entered in the screening log. Patients with an Impella® device must have the device removed during HMII implant to be enrolled into the study.

Qualified subjects who have provided consent will be entered in the appropriate EDC CRF, which must be submitted to the Sponsor after the patient has been screened and prior to enrollment, or no later than 48 hours post implantation. Notification of enrollment to the Sponsor will only take place when the consented subject has been entered in the EDC. Enrollment information (name of the study, date of consent, and inclusion/exclusion criteria) will be recorded in the subject's hospital records.

If a consented subject does not meet all eligibility criteria at the time of implant; does not receive a HM II LVAD; experiences a serious adverse event in the perioperative period that the investigator feels would compromise the patient's participation in the trial (e.g., debilitating stroke); or expires during the implant procedure, then the subject will not be enrolled or contribute to the study endpoints. The reason for ineligibility at the time of

Clinical Investigational Plan

implant will be recorded in the screening log. The subject is enrolled upon successful implantation of the HM II and randomization per **Section 4.10**.

6.4 BASELINE VISIT

The following baseline assessments will be performed:

Table 2 – Baseline Data Collection

Study Activity	Data Collection
Informed Consent	Informed consent details
Inclusion/Exclusion	Subject's eligibility details
Demographics	Age, gender, ethnicity, race, blood type, INTERMACS profile, and NYHA class
General and Cardiac Medical History	Etiology of HF, duration of HF, indication (BTT/DT), arrhythmias, prosthetic valve(s), stroke, diabetes, smoking, history of bleeding (diverticular disease, diagnosed arteriovenous malformations (AVMs), GI ulcer(s), anemia, and/or erythropoietin treatment), aortic stenosis, hypertension, history of MI, peripheral thromboembolism, coronary stents, CABG, substance abuse (drug/alcohol), drug/radiation toxicity, peripheral vascular disease, carotid artery disease, cardiac rhythm management device, intra-aortic balloon pump, CardioMEMS, and HIV
Vital Signs	Height, weight, blood pressure, and heart rate
Anticoagulation/Antiplatelet Medications	Warfarin, clopidogrel, dipyridamole, other anticoagulation agents, other vitamin K antagonists, direct thrombin inhibitors, etc (including research drug). All new medications started, or current medications stopped during the follow-up period must be recorded. All dose changes (including IV titrations) during the follow-up period must be recorded with the exclusion of Warfarin/Coumadin. Only the start and stop dates will be collected for Warfarin/Coumadin
Other Medications	ACE inhibitors, inotropes, ARBs, beta blockers, antiarrhythmics, statins, nitrates, allopurinol, aldosterone blockers, antibiotics, diuretics, insulin and antidiabetic medications, and other cardiovascular medications
¹ Laboratory Assessments	Hemoglobin (Hgb), Hematocrit (Hct), White Blood Cell Count (WBC), Platelets (PLT), Creatinine (Cr), Estimated Glomerular Filtration Rate (eGFR), LDH and INR. For diabetic patients: HbA1c, and fasting glucose Collected only if SOC: Activated Partial Thromboplastin Time (aPTT), Partial Thromboplastin Time (PTT), Plasma free Hgb (PHgb), liver function tests (AST, ALT, total bilirubin, albumin, pre-albumin), blood urea nitrogen (BUN), D-Dimers, P Selectin, and fibrinogen
ASA Resistance Testing	ASA resistance testing (e.g. TEG® PlateletMapping®, VerifyNow®, etc.) Note: To protect blinding of the study, platelet function testing (including ASA resistance testing) should be avoided during the course of the study except where indicated by the CIP.
² Coagulation Assessment	Tests may include but are not limited to HIT, protein C deficiency, protein S deficiency, antithrombin deficiency, plasminogen deficiency, lupus anticoagulant, factor V Leiden, prothrombin G20210A mutation, and primary antiphospholipid syndrome
² Right Heart Catheterization	Central venous pressure (CVP) or right atrial pressure (RAP), systolic, diastolic and mean pulmonary artery pressure (PAS, PAD, PAM), pulmonary capillary wedge pressure (PCWP), cardiac output (CO), and cardiac index (CI)
² Echocardiogram	Type of assessment, LVEF, LVEDD, LVESD, AI, MR, TR, PR, including severity and/or grade, and presence of LV or LA thrombus, and aortic valve opening ratio, including percent AV area opening, and AV opening time

¹ Most recent results obtained within 30 days prior to implant will be permitted as baseline data

² If collected per standard of care, most recent results within 30 days prior to implant.

Clinical Investigational Plan

6.5 IMPLANT PROCEDURE

The following data will be collected for each subject's HM II implant procedure.

Table 3 – Implant Procedure Data Collection

Study Activity	Data Collection
HM II System Information	VAD serial number, reference number and date of implant of entire implanted system
Implant Data	Signs of infection prior to implant, location of outflow anastomosis, apical cuff attachment method, driveline location and positioning, percutaneous driveline exit type, initial pump parameters, presence of LV or LA thrombus, concurrent procedures, Factor VII administration, vitamin K administration, anti-fibrinolytic administration, pump position, transfusions (whole blood, packed red blood cells [PRBC], fresh frozen plasma [FFP], platelets, cryoprecipitate, Cell Saver), cardiopulmonary bypass (CPB) time, and total implant time, procedure completion time
Adherence to PREVENT Recommended Practices	Pump pocket size, pump pocket location (inferiorly deep and lateral), inflow cannula position, outflow graft position, pump position, pump fixation, pump speed management, post-operative anticoagulation/antiplatelet management (including Heparin bridging) and blood pressure management
Pump Parameters	Pump Speed, Pump Flow, Pulsatility Index, and Pump Power
Randomization	Confirmation of randomization, date of randomization, and date that research drug was started following implant
Research Drug Bottle Dispensing	Bottle number of the research drug dispensed and date dispensed.

6.6 SCHEDULED FOLLOW-UP VISITS

The required assessments, follow-up schedule, and associated visit windows are generally aligned with INTERMACS, a national MCS registry. All follow-up visits are based on the initial implant date, even if a pump exchange occurs while the subject is being followed on the study. The windows for each follow-up visit are as follows:

Table 4 – Follow-Up Visit Windows

Baseline	Implant	Visit 1	Visit 2	¹ Visit 3	¹ Visit 4	¹ Visit 5	¹ Visit 6
-	-	Week 1 ± 3 days	Month 1 ± 7 days	Month 3 ± 20 days	Month 6 ± 20 days	Month 9 ± 20 days	Month 12 ± 20 days

¹ Note that the window for these visits have been shortened to ± 20 days from the original INTERMACS ± 30 days window.

The follow-up visit must occur within the designated window. Follow-up assessments for a single visit do not have to occur on the same date, but must occur within the designated window, or will be considered a CIP deviation. The Sponsor understands that some lab results may be received several days after the visit has occurred.

At the completion of the Month 12 visit, the subject has completed the study. With the exception of some lab results that may be received after the visit has occurred, no other assessments or study related activities may be performed after the final visit has occurred, even if later assessments are performed within the acceptable window. Month 12 assessments not collected by the date of the final visit will be considered a protocol deviation.

Clinical Investigational Plan

Table 5 – Scheduled Follow-Up Visit Data Collection

Study Activity	Definition
Subject Status	Initial discharge status, and visit completion
Vital Signs	Weight, blood pressure and method of blood pressure measurement
Pump Parameters	Pump Speed, Pump Flow, Pulsatility Index, and Pump Power
Cardiac Arrhythmias	Atrial (fibrillation/flutter), ventricular (fibrillation/VT), and treatment
Anticoagulation / Antiplatelet Medications	All changes made during the follow-up period All new medications started, or current medications stopped during the follow-up period must be recorded. All dose changes (including IV titrations) during the follow-up period must be recorded with the exclusion of Warfarin/Coumadin. Only the start and stop dates will be collected for Warfarin/Coumadin
Other Medications	ACE inhibitors, inotropes, ARBs, beta blockers, antiarrhythmics, statins, nitrates, allopurinol, aldosterone blockers, antibiotics, diuretics, insulin and antidiabetic medications, and other cardiovascular medications
Bottle Dispensing	All bottles dispensed during the follow-up period (Month 3, 6 and 9 follow-up visits only), including replacement bottles that are dispensed outside of the follow-up schedule,
Bottle and Unused Research Drug Return	Bottle status and shipping information. All bottles and unused doses must be returned to ALMAC Clinical upon receipt from subject.
Laboratory Assessments	Hemoglobin (Hgb), Hematocrit (Hct), White Blood Cell Count (WBC), Platelets (PLT), Creatinine (Cr), Estimated Glomerular Filtration Rate (eGFR), LDH and INR. For diabetic patients: HbA1c, and fasting glucose Collected only if SOC: Activated Partial Thromboplastin Time (aPTT), Partial Thromboplastin Time (PTT), Plasma free Hgb (PHgb), liver function tests (AST, ALT, total bilirubin, albumin, pre-albumin), blood urea nitrogen (BUN), D-Dimers, P Selectin, fibrinogen, and Anti Factor Xa Assay (Heparin Assay). Note: To protect blinding of the study, platelet function testing (including ASA resistance testing) should be avoided during the course of the study except where indicated by the CIP.
Adherence to PREVENT Recommended Practices	Blood pressure management, INR goals, and pump speed management
Chest/Abdominal X-Ray	PA and lateral chest/abdominal X-rays (that show the entire pump relative to major cardiac/anatomical structures) will be submitted to Sponsor for independent analysis of pump position Note: Collected between Implant and Month 1 visits, or at pump thrombosis or pump exchange events
¹ Echocardiogram	LVEF, LVEDD, LVESD, AI, MR, TR, PR, including severity and/or grade, and presence of LV or LA thrombus, and aortic valve opening ratio, including percent AV area opening, and AV opening time

¹ If collected per SOC.

Clinical Investigational Plan**6.7 UNSCHEDULED VISITS****6.7.1 OPERATIVE PROCEDURES**

Data related to any cardiac or non-cardiac operative procedures occurring after enrollment will be collected. Operative procedures must be reported to the Sponsor through the EDC system immediately upon discovery of the event or, at the latest, if the operation is unknown to the implanting site (i.e. at another facility), during the next follow-up visit.

For pump exchanges (HM II to HM II only), additional Pump Exchange data will be collected, including exchange status, implant data, PREVENT recommended practices and Chest/Abdominal X-ray. In the event of a pump exchange, the follow-up visit schedule will continue to be based on the initial implant date.

6.7.2 REHOSPITALIZATIONS

All hospitalizations extending over 24 hours with associated reasons will be captured during the follow-up period for all subjects. While hospitalized, the follow-up visit assessments will continue to be performed according to the follow-up schedule. Rehospitalizations must be reported to the Sponsor through the EDC system immediately upon discovery of the event or, at the latest, if the rehospitalization is unknown to the implanting site (i.e. at another facility), during the next follow-up visit.

6.7.3 OUTCOMES

Subjects will be followed for 12 months or until an outcome is reached, whichever occurs first. Outcomes include death, heart transplantation, explant (except in cases of HM II to HM II pump exchange), and withdrawal from the study. Outcomes must be reported to the Sponsor through the EDC system immediately upon discovery of the event.

If a subject receives a pump exchange (HM II to non-HM II) during the follow-up period, this event will be considered an explant outcome. If a subject receives a pump exchange (HM II to HM II) during the follow-up period, the subject will remain in the study on the original follow-up schedule.

If a subject has a device explanted for confirmed or suspected pump thrombosis, the pump will be returned to the Sponsor for analysis. Standard commercial processes should be used for pump return.

6.8 SUBJECT STUDY COMPLETION

When the subject has completed the study, the physician will resume management per SOC. To preserve blinding for investigators and remaining enrolled subjects, the research drug arm assignments of individual subjects will not be disclosed until all subjects at the respective site have completed the study.

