Maximum follow-up duration per subject will be 12 months. Primary endpoints will be evaluated at 6 months. Individual components of the primary endpoints along with the descriptive endpoints will be evaluated at 12 months.

Clinical Investigational Plan

Study Synopsis

Statistical Considerations	
Primary Efficacy Endpoint Analysis – Reduction of Bleeding: The rate of non-surgical bleeding at 6 months will be compared between the Treatment and Control Arms utilizing the Fisher’s Exact Test. The primary endpoint for efficacy will be assumed to be met if the p-value < 0.05. The assumption is that there will be a 15% rate reduction at 6 months.
 
A sample size of 330 subjects (165 in each arm) with an alpha of 0.05 will provide 80% power to demonstrate a significant difference between the Treatment and Control Arms.
 
Primary Safety Endpoint Analysis – Non-Inferiority of Stroke and Thrombus: The difference in the rates of the composite endpoint of stroke and pump thrombosis between Treatment and Control Arms and the 95% confidence limit of the difference will be evaluated. If the upper confidence limit of the difference is < 10% then the non-inferiority criterion will be considered to have been met.
 
A sample size of 338 subjects (169 in each arm) will provide 80% power, with a target alpha of 0.025 (because this will be a one-sided test on the upper confidence limit) to demonstrate non-inferiority of the Treatment Arm to the Control Arm.
 
A total study sample size of 350 subjects will provide enough statistical power to demonstrate both efficacy and safety of the warfarin only anticoagulation regimen in these patients.
 
Both primary endpoints must be met for the study to be successful.
 
Intermediate Safety Assessment: A safety assessment will be performed after 60 subjects have completed 3 months of follow-up. Both incidence of stroke and pump thrombosis will be analyzed and results will be presented to the Steering Committee. Additionally, after the initial 3-month safety review, an analysis of AEs associated with primary endpoints will be presented to the Steering Committee for continued safety assessment in regular 6-month intervals. The Steering Committee will review the findings and make a decision to proceed or stop the study due to safety concerns.

Devices Used	HM II Left Ventricular Assist Device (LVAD)

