4.3 STUDY BLINDING

The subjects and the investigators will be blinded to the subject's research drug assignment. Un-blinding will not be performed unless the subject is experiencing a major allergic reaction potentially attributable to the research drug. If a major allergic reaction occurs, the subject should be medically managed per standard of care. Un-blinding will occur only with approval from the Steering Committee and will be documented. Requests for unblinding will be answered within three business days of the request. If un-blinding occurs, the subject will be withdrawn from the study.

Clinical Investigational Plan**4.3.1 DESCRIPTION OF SUBJECT POPULATION**

All subjects receiving a HM II implant in accordance with the approved indications for use (BTT or DT) will be considered for this study, regardless of gender, race, or ethnicity.

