4.3.3 NUMBER OF SUBJECTS REQUIRED TO BE INCLUDED IN THE STUDY

A total sample size of up to 350 subjects will be enrolled. Subjects enrolled into the study will be randomized in a 1:1 fashion and randomization will be stratified by study site and blocked to maintain a 1:1 ratio over time.

Subjects will be followed up to 12 months with the primary endpoints evaluated at 6 months. The study will be conducted at up to 45 sites, and up to 45 subjects may be enrolled at any site. An enrollment increase may be requested by individual sites, and approval will be granted at the discretion of the Sponsor.

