4.3.4 ESTIMATED TIME NEEDED TO ENROLL SUBJECT POPULATION

Based on the anticipated enrollment rate, the estimated time needed to enroll this subject population is approximately 2.75 years.

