8.2 ADHERENCE TO THE CLINICAL INVESTIGATION PLAN

A deviation is defined as an event in which the investigator, site personnel, Sponsor or Sponsor representative did not conduct the study in accordance with the CIP, IRB requirements, or the Investigator Agreement. The investigator is not allowed to deviate from the CIP, which includes inclusion/exclusion criteria and protection of subject safety, except as specified under emergency circumstances. Investigators and sites agreeing to participate in the study must believe that there is equipoise for randomization, and must be willing to be blinded for the duration of the study at their site. Un-blinding will not be performed unless subject is experiencing a major allergic reaction potentially attributable to the research drug, and will require Steering Committee approval. If the study drug is un-blinded, then the subject will be withdrawn from the study.

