12 STATISTICAL CONSIDERATIONS

PREVENT II is a prospective, multi-center, randomized, double-blinded, placebo-controlled study evaluating the risk of subjects over 50 years of age being managed on warfarin therapy alone compared to warfarin and ASA therapy together. The two groups in the study are as follows:

- 1) Treatment Arm: Warfarin (INR target: 2.0-2.5, median: 2.25) + Placebo (1 pill/day)
- 2) Control Arm: Warfarin (INR target: 2.0-2.5, median: 2.25) + ASA therapy (81mg/day)

In general, continuous data will be presented as the number of subjects, mean with standard deviation, median, minimum, and maximum values. Categorical data will be reported as frequencies and percentages. Adverse events will additionally be reported as events per subject year, with only those events that start after implantation of the HM II analyzed. The adverse events will be compared between the two arms of the study using risk ratios (Poisson's regression). Survival data will be presented and analyzed using the Kaplan-Meier method.

The primary endpoints will be analyzed per protocol method as defined in **Section 12.1**. Every effort will be made to avoid crossovers, but in such instances, analysis will be performed in accordance with **Section 12.1**. The study will be conducted in a double-blinded fashion with neither the investigator, nor the subject having the knowledge of whether the subject is in the Treatment or the Control Arm. Only the primary statistician from the Sponsor will have knowledge of the specific groups, and all other parties will be blinded.

Every effort will be made to collect all required data. A one-sided 0.025 level of significance or two-sided 0.05 level of significance will be used to declare statistical significance as outlined below. Multiplicity adjustments will not be made unless specified below. A sensitivity analysis will be performed to account for any bias that may have been introduced by subjects withdrawing from the study or being removed from the study.

Clinical Investigational Plan**12.1 STATISTICAL DESIGN, HYPOTHESES, METHOD AND ANALYTICAL PROCEDURES**

Subjects will be block randomized per site on a 1:1 ratio into the Treatment and Control Arms. The study is designed to satisfy two primary endpoints. Both primary endpoints must be met for the study to be successful.

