12.4 RANDOMIZATION APPROACH

Subjects will be randomized in a 1:1 fashion (one Treatment Arm subject to one Control Arm subject). The randomization will be stratified by study site and blocked to maintain the 1:1 ratio over time. The Sponsor will implement randomization through ALMAC Clinical's WebEZ system. Randomization will occur after the subject is successfully implanted with the HM II, and must be completed within 48 hours of implant.

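### Section 6.8 lets arm assignments be disclosed once a single site has finished, instead of waiting for trial-wide completion, final adjudication and database lock

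*Combined protocol and SAP*

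**What the plan says.** Four places in the protocol bear on when the blind ends.

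- **Section 6.8** governs subjects who have finished. After completion the physician returns to usual care, and "the research drug arm assignments of individual subjects will not be disclosed until all subjects at the respective site have completed the study". The stated aim is to protect blinding of investigators and of subjects still enrolled.
- **Section 8.2** says that participating investigators and sites "must be willing to be blinded for the duration of the study at their site".
- **Section 12** says: "Only the primary statistician from the Sponsor will have knowledge of the specific groups, and all other parties will be blinded". It gives no date or event at which this ends.
- **Section 4.3** covers un-blinding of a subject during the study: "Un-blinding will not be performed unless the subject is experiencing a major allergic reaction potentially attributable to the research drug". Steering Committee approval is required.

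Section 12.4 adds that "The randomization will be stratified by study site and blocked to maintain the 1:1 ratio over time". Sections 12.1.1, 12.1.2 and 14 give the CEC the adjudication of bleeding and thromboembolic events, including whether a hemorrhagic stroke counts toward the efficacy or the safety endpoint. No section makes disclosure depend on completion at all sites, on the end of adjudication or on database lock.

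**The concern.** In a double-blind trial, individual assignments are normally held until the data of the whole trial are final. Here the only stated condition is local. Site staff already know their own subjects' outcomes, so once they have the assignments they also have that site's results by arm.

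Two things are at stake. The first is the site's own data. Section 7.1.3 lets the sponsor ask for source documents, and the main endpoint components need judgement: what counts as non-surgical bleeding, and whether a hemorrhagic stroke is primary or follows ischemic conversion or treatment of a thrombosis event. A site that knows the arm may still be answering queries and supplying documents on these questions. The second is the rest of the trial. By-arm experience could pass informally to investigators who are still enrolling and reporting events, and who under Section 8.2 must believe there is equipoise. It could also reach the Steering Committee, which under Section 12.3 decides whether the study continues.

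**Working it through.** The plan states no figure on this point, so there is none to reproduce. The check has two parts: what the text permits, and whether release could fall well inside the running trial.

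**1. Text.** Sections 6.8 and 8.2 both use the site as the unit. Section 12 names who may know the arms but not for how long. Section 4.3 deals with un-blinding on account of an allergic reaction and does not address release after completion. Read together, nothing forbids release to a finished site while other sites are active.

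**2. Timeline.** Inputs:
- Accrual (Section 4.3.4): "the estimated time needed to enroll this subject population is approximately 2.75 years", so 2.75 × 12 = 33 months.
- Follow-up (Synopsis): "Maximum follow-up duration per subject will be 12 months".
- Size (Section 4.3.3): "A total sample size of up to 350 subjects will be enrolled", at up to 45 sites.

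The last final visit falls near month 33 + 12 = 45. A site whose last subject enters at month m completes at month m + 12. Its lead over the end of the trial is 45 − (m + 12) = 33 − m months. Accrual still to run elsewhere at that moment is 33 − (m + 12) = 21 − m months, if positive.

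| Last entry at the site (month) | Site complete (month) | Lead before last final visit (months) | Accrual still to run elsewhere (months) |
|---|---|---|---|
| 6 | 18 | 27 | 15 |
| 12 | 24 | 21 | 9 |
| 18 | 30 | 15 | 3 |
| 24 | 36 | 9 | 0 |

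**3. How many sites this could touch.** The documents give no accrual pattern by site, so this step rests on assumptions: 350 subjects entering uniformly over 33 months, all sites open from the start, 20, 30 or 45 sites, site sizes equal or skewed (gamma weights), every subject followed for 12 months, and 1,000 simulated trials per setting.

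| Sites | Sizes | Finish at least 6 months before the last final visit | Subjects at those sites | Finish before the trial's last enrollment | Median lead (months) |
|---|---|---|---|---|---|
| 45 | equal | 23.6% | 19.4% | 5.7% | 2.9 |
| 45 | skewed | 33.0% | 13.8% | 16.1% | 3.4 |
| 30 | equal | 11.6% | 9.5% | 1.4% | 1.9 |
| 30 | skewed | 25.9% | 8.4% | 11.8% | 2.4 |
| 20 | equal | 3.8% | 3.1% | 0.1% | 1.3 |
| 20 | skewed | 18.4% | 4.4% | 8.4% | 1.7 |

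Under these assumptions, 4% to 33% of enrolling sites finish at least 6 months early, and 0.1% to 16% finish before the last subject in the trial is enrolled. The typical site finishes only 1 to 3 months early, so the exposure lies with a minority of sites.

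**4. What one site would learn.** At 45 sites the average is 350 / 45 = 7.8 subjects, or about 4 per arm. A site at the 45-subject cap would hold 45 / 350 = 12.9% of the sample.

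**The case against.** The strongest reply is that Section 6.8 is a floor. It bars disclosure before a certain moment and does not require or schedule disclosure then. A sponsor that waits until the whole study is over complies with it. That is right, and it limits the point to what the text permits.

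Second, the harm is bounded. Once a site's subjects have completed, knowing the arm cannot change how they are treated in the study. Stratification by site means that one site's list says nothing about assignments at another. About four subjects per arm at an average site is little evidence. The CEC, not the site, makes the final attribution, and Section 6.8 does not provide for release to the CEC or the Steering Committee. All of this stands. What remains is that the CEC works from what sites report and document, that nothing requires this to be final before release, and that informal leakage is not excluded.

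Two stronger readings are tempting, and the documents do not support either:

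- A reader might infer that Sections 6.8 and 12 contradict each other. They do not: both are obeyed if release waits until the end of the study. Section 12 simply gives no end date.
- A reader might infer that a site with no active subject, but still open to enrollment, could be given its past assignments and so predict later ones from its blocks. Section 8.2 keeps investigators blinded for as long as the study runs at their site, and a site still enrolling has not ended the study there. The stated aim of Section 6.8 points the same way. The natural meaning of its condition is every subject the site will enroll.

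**Conclusion.** The concern holds in a limited form. The protocol permits arm assignments to be disclosed site by site, before the trial as a whole is complete, adjudicated and locked. For a site whose last subject enters at month 12, disclosure could come about 21 months before the last final visit, with about 9 months of enrollment still to run elsewhere. The month figures rest on the planned 33-month accrual being met and on full 12-month follow-up. The shares of sites affected rest on the assumed accrual pattern and show plausibility only.

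The risk is to the objectivity of late query and source-document responses and to the confidentiality of by-arm experience. It is not a risk to allocation concealment at other sites, and the documents do not show that early release is intended. This is an inexpensive improvement to the wording and not a flaw that undermines the design.

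**What to change.** Reword Section 6.8 so that no individual arm assignment is disclosed to sites, subjects, the CEC or the Steering Committee until three conditions are met: all subjects at all sites have completed, CEC adjudication is final, and the database is locked. The only exception should be un-blinding as Section 4.3 already provides, by cross-reference and not by a newly worded exception. Change Section 8.2 so that the investigator's commitment to remain blinded runs to the same point, and give the blinding statement in Section 12 the same end date.

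The change costs a sentence in each place. The downside is that subjects and physicians at early-finishing sites wait longer to learn the assignment: in the month-12 example, about 21 months plus the time for adjudication and lock. Section 6.8 already has subjects return to usual care without that information whenever others at their site are still in the study, so the change lengthens an existing wait and does not create a new one.
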